5.3. Safety Reporting

Safety parameters specified as primary and secondary endpoints will be summarized using IDSL standard reporting shells as indicated in Section 5.7.3.

5.4. Pharmacokinetic Reporting

GSK GSK2879552 concentrations pre-dose and post-dose will be summarized using IDSL standard reporting shell as indicated in Section 5.7.4.

5.5. Data Display Numbering

The following numbering will be applied for RAP generated displays:

Section	Tables	Figures
Study Population	1.1 to 1.5	
Efficacy	2.1 to 2.8	
Safety	3.1 to 4.10	
Section	Listings	
ICH Listings	1 to 32	

5.6. Mock Example Shell Referencing

Non IDSL specifications will be referenced as indicated.

Section	Figure	Table	Listing
Study Population			POP_Ln
Safety		SAFE_Tn	SAFE_Ln
Efficacy	EFF_Fn	EFF_Tn	EFF_Ln
Pharmacokinetic		PK_Tn	PK_Ln

NOTES:

- Non-Standard displays are indicated in the 'IDSL / Example Shell' or 'Programming Notes' column as '[Non-Standard] + Reference.'

5.7. Deliverables

Delivery [Priority] [1]	Description
SAC [X]	Final Statistical Analysis Complete

NOTES:

1. Indicates priority (i.e. order) in which displays will be generated for the reporting effort

5.7.1. Study Population Tables

Study Population Tables					
No.	Population	IDSL / Example Shell	Title	Programming Notes	Deliverable [Priority]
Subject Disposition					
1.1.	All treated	ES1	Summary of Participant Disposition for the Participant Conclusion Record	ICH E3, FDAAA, EudraCT	SAC [1]
1.2.	All treated	NS1	Summary of Number of Participant by Country and Site ID	EudraCT/Clinical Operations	SAC [1]
Demographic and Baseline Characteristics					
1.3.	All treated	DM1	Summary of Demographic Characteristics	ICH E3, FDAAA, EudraCT	SAC [1]
1.4.	All treated	DM11	Summary of Age Ranges	EudraCT	SAC [1]
1.5.	All treated	DM5	Summary of Race and Racial Combinations	ICH E3, FDA, FDAAA, EudraCT	SAC [1]

5.7.2. Efficacy Tables: Clinical Activity

Efficacy: Tables					
No.	Population	IDSL / Example Shell	Title	Programming Notes	Deliverable [Priority]
Efficacy Tables: Clinical Activity					
2.1.	All treated	RE1a	Summary of Investigator-Assessed Best Response (Without Confirmation) (IMWG 2016)	
FDAAA, EudraCT Notes: Summarize by arm; Do not include Total. Best Response: Complete response (CR), molecular Complete Remission (mCR), Partial Response (PR), Cytogenetic Response, Hematologic Improvement (HI), or Stable Disease (SD), Not Evaluable (NE). Add a category of 'Missing' if summarize for Unconfirmed response. Objective Response Rate (ORR): % of subjects achieving CR, mCR, PR, Cytogenic Response, or HI. Clinical Benefit Rate (CBR): % subjects achieving CR, mCR, PR, Cytogenic Response, HI, or SD. Include: ORR and CBR (No p-value) in one table.
	SAC [1]

Efficacy: Tables					
No.	Population	IDSL / Example Shell	Title	Programming Notes	Deliverable [Priority]
2.2.	All treated	RE1a	Summary of Investigator-Assessed Best Response (With Confirmation) (IMWG 2016)	FDAAA, EudraCT Note: See comments above for table 2.1.	SAC [1]
2.3.	All treated	TTE1	Summary of Progression-free Survival	FDAAA, EudraCT	SAC [1]
2.4.	All treated	TTE1a	Summary of Duration of Response	FDAAA, EudraCT	SAC [1]
2.5.	All treated	TTE1	Summary of Overall Survival	FDAAA, EudraCT	SAC [1]
2.6.	All treated	TTE1a	Summary of Time to AML	FDAAA, EudraCT	SAC [1]
2.7.	All treated	BPA1	Summary of Documented Platelet Transfusions	FDAAA, EudraCT	SAC [1]
2.8.	All treated	BPA1	Summary of Documented RBC Transfusions	FDAAA, EudraCT	SAC [1]

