2. SUMMARY OF KEY PROTOCOL INFORMATION - STUDY OBJECTIVE(S) AND ENDPOINT(S)

2.1.1. Part 1: Dose Confirmation and Escalation

Objectives	Endpoints
Primary Objectives	Primary Endpoints

 To determine the recommended phase 2 dose (RP2D) of GSK2879552 administered alone and in combination with Azacitidine in adult subjects with HR MDS previously treated with HMA. 	
 AEs, SAEs, dose limiting toxicities, dose reductions or delays, withdrawals due to toxicities and changes in safety parameters (e.g., laboratory values, vital signs, electrocardiograms [ECGs], physical examinations).
Secondary Objectives	Secondary Endpoints

 To evaluate clinical activity after treatment with GSK2879552, alone or in combination with 	
 Clinical benefit rate (CBR) defined as % of subjects achieving CR, mCR, PR, HI or SD. Objective response rate (ORR)

Objectives	Endpoints
Azacitidine, in adult subjects with HR MDS previously treated with HMA.	defined as % of subjects achieving CR, mCR, PR, or HI [as per 2006 IWG criteria].

 To measure the exposure to GSK2879552 alone and to GSK2879552 and Azacitidine in combination, in patients with HR MDS previously treated with HMA. 	
 GSK2879552 and Azacitidine concentrations pre-dose and post-dose.

 To evaluate duration of response, duration of clinical benefit, progression-free survival and overall survival. 	
 Duration of response (DOR) defined as the time from first documented response to disease progression. Progression-free survival (PFS) defined as the time from first dosing day to disease progression or death from any cause. Overall survival (OS) defined as the time from first dosing day until death from and cause.

 To evaluate frequency and time to progression to AML (per 2006 IWG criteria). 	
 Proportion of subjects with disease progression to AML. Time to AML progression.

 To evaluate platelet and RBC transfusion dependence. 	
 Number of documented platelet and RBC transfusions per month prior to study entry and on study.
Exploratory Objectives	Exploratory Endpoints

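### The only ORR and CBR tables cite different response criteria, redefine mCR and count cytogenetic response, against the SAP's own endpoint definition

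*SAP*

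**What the plan says.** Section 2.1.1 gives the Part 1 secondary endpoint: ORR is "defined as % of subjects achieving CR, mCR, PR, or HI [as per 2006 IWG criteria"; CBR adds SD. Section 2.1.2 repeats this for Part 2, which was not started. Section 5.2 adopts the 2006 IWG criteria, spells out mCR as marrow complete remission, lists the same components for ORR and CBR, and uses the same four response categories to pick the responders for duration of response (DOR). Its criteria table has a marrow CR row based on marrow blasts, and no cytogenetic or molecular row.

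Section 5.7.2 specifies the displays differently:

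- Table 2.1 is titled "Summary of Investigator-Assessed Best Response (Without Confirmation) (IMWG 2016" and Table 2.2 "Summary of Investigator-Assessed Best Response (With Confirmation) (IMWG 2016". Listing 27 in Section 5.7.5 carries the same IMWG 2016 label.
- The Table 2.1 note expands the abbreviation as "molecular Complete Remission (mCR".
- The note defines the rates as "Objective Response Rate (ORR): % of subjects achieving CR, mCR, PR, Cytogenic Response, or HI" and "Clinical Benefit Rate (CBR): % subjects achieving CR, mCR, PR, Cytogenic Response, HI, or SD".
- Table 2.2 takes the note over: "Note: See comments above for table 2.1".

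**The concern.** Section 5.2 sends the efficacy endpoints to Section 5.7.2 for display, so a programmer will build the tables from the note. Followed literally, it credits the rates to criteria that the analysis text does not use, changes what mCR means, and widens both numerators by a category for which the SAP has no definition. The disclosed ORR could then differ from the endpoint as defined. On the same confirmation basis, the responders counted in Table 2.1 or 2.2 could also differ from those entering the DOR analysis in Table 2.4. No other table reports ORR or CBR, so no correctly specified version exists to fall back on.

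**Working it through.** There is no plan figure to reproduce, because the conflict involves no sample size, power or event count. The check sets the definitions side by side.

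| Item | Sections 2.1.1 and 5.2 | Section 5.7.2, Table 2.1 note and Table 2.1/2.2 titles |
|---|---|---|
| Criteria | IWG 2006 | IMWG 2016 |
| mCR | marrow | molecular |
| ORR | CR, mCR, PR, HI | CR, mCR, PR, cytogenetic, HI |
| CBR | ORR components plus SD | the same plus cytogenetic |
| DOR responders (Section 5.2) | CR, mCR, PR, HI | not redefined |

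The left column agrees with itself throughout on components; the right column departs from it in every row that it fills. Section 5.2 also says that the response types to be produced are those of its criteria table, so the note cannot be read as a compatible elaboration of that text.

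**Effect of the extra category.** The SAP does not state the number treated, so N is assumed. One subject who qualifies on cytogenetic response alone adds 1/N to ORR. The illustration starts from no other responder and uses exact (Clopper-Pearson) 95% intervals. For 0/N the upper limit is 1 − 0.025^(1/N). For 1/N the lower limit is 1 − 0.975^(1/N), and the upper limit is the 97.5% point of a beta distribution with parameters 2 and N − 1.

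| Assumed N | ORR without the subject (95% CI) | ORR with the subject (95% CI) | Shift |
|---|---|---|---|
| 6 | 0% (0 to 45.9%) | 16.7% (0.4 to 64.1%) | 1/6 = 16.7 points |
| 10 | 0% (0 to 30.8%) | 10.0% (0.3 to 44.5%) | 1/10 = 10.0 points |
| 20 | 0% (0 to 16.8%) | 5.0% (0.1 to 24.9%) | 1/20 = 5.0 points |

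**Effect on CBR.** The shift is 1/N only if that subject has not also met stable disease, which the criteria table ties to more than 8 weeks without progression. Otherwise it is 0.

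**Effect of the mCR wording.** If *molecular* were applied literally, a subject whose only response is a marrow CR could drop out of the numerator, lowering ORR by 1/N. The two errors can therefore act in opposite directions.

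**No effect.** With no cytogenetic-only responder, and mCR programmed from the marrow criterion, both rates are unchanged.

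**The case against.** The three discrepancies do not weigh the same. The IMWG 2016 titles and the word *molecular* look like slips: Section 5.2 names the criteria and gives the marrow blast threshold, so a careful programmer might well get mCR right. Only the cytogenetic category openly adds something to a rate. Even there the effect is hypothetical, since the SAP does not show whether investigators recorded cytogenetic response at all. The assumed values of N illustrate 1/N and say nothing about this trial. The study also stopped early, and these are secondary endpoints. Section 5 says that there is a single treatment group and the note says "Include: ORR and CBR (No p-value) in one table", so no test result depends on the definition, although Section 5.2 still mentions a chi-square or Fisher test. Finally, Section 5.2 is not perfectly uniform itself: its CBR sentence asks for confirmation of some responses and its ORR sentence does not.

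Most of this stands as a limit on importance. It does not remove the conflict. The component lists in Sections 2.1.1 and 5.2 agree whatever the confirmation wording, and no text says that the note overrides them. Early termination is no excuse either, because Section 3 still commits to summarising the Part 1 secondary endpoints.

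**Conclusion.** The concern holds. The specification of Tables 2.1 and 2.2 contradicts the SAP's own endpoint definition in criteria label, meaning of mCR and content of both numerators. The cytogenetic category carries most of the weight; the other two are label corrections that belong with it. The size is conditional: ORR moves by 1/N for each subject classified differently, CBR by 1/N or not at all, and both by zero if no subject is affected. The SAP gives neither N nor response counts, so the actual effect cannot be computed. This should be fixed before the tables are produced, as a correction for consistency in disclosed descriptive rates. It does not threaten a primary conclusion.

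**What to change.** In the titles of Tables 2.1 and 2.2 and Listing 27, replace the IMWG 2016 label with IWG 2006 as modified in Section 5.2. In the Table 2.1 note, change *molecular* to *marrow* and take cytogenetic response out of the ORR and CBR numerators. If it was collected, it can appear as a separate descriptive line outside both rates.

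If the sponsor does intend cytogenetic response to count, the Section 5.2 definitions, its criteria table and the DOR responder definition must all change together, with an explicit criterion. Section 2.1.1 summarises the protocol endpoint, so this should be declared as a departure from that endpoint and not written in silently.

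The first option costs edits to three titles and one programming note. It needs no new data.

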5.7.3. Safety Tables

Safety: Tables					
No.	Population	IDSL / Example Shell	Title	Programming Notes	Deliverable [Priority]
Adverse Events (AEs)					
3.1.	All treated	AE15	Summary of Common ($\geq X\%$) Non-serious Adverse Events by System Organ Class and Preferred Term (Number of Participant and Occurrences)	FDAAA, EudraCT X% will be set to 0% so table will include all Non-serious AEs	SAC [1]
3.2.	All treated	AE16	Summary of Serious Adverse Events by System Organ Class and Preferred Term (Number of Participants and Occurrences)	FDAAA, EudraCT	SAC [1]
3.3.	All treated	DL1	Summary of Dose-Limiting Toxicities during the Determinative Period	FDAAA, EudraCT	SAC [1]
Laboratory Parameters					

Safety: Tables					
No.	Population	IDSL / Example Shell	Title	Programming Notes	Deliverable [Priority]
3.4.	All treated	LB1	Summary of Chemistry Changes from Baseline	FDAAA, EudraCT	SAC [1]
3.5.	All treated	LB1	Summary of Haematology Changes from Baseline	FDAAA, EudraCT	SAC [1]
3.6.	All treated	LB1	Summary of Coagulation Changes from Baseline	FDAAA, EudraCT	SAC [1]
3.7.	All treated	LB1	Summary of Urinalysis Changes from Baseline	FDAAA, EudraCT	SAC [1]
3.8.	All treated	LIVER1	Summary of Liver Monitoring/Stopping Event Reporting	FDAAA, EudraCT	SAC [1]
Vital Signs					
3.9.	All treated	Vs1	Summary of Change from Baseline in Vital Signs	FDAAA, EudraCT	SAC [1]
ECG					
3.10.	All treated	EG2	Summary of Change from Baseline in ECG Values by Visit	FDAAA, EudraCT	SAC [1]

5.7.4. Pharmacokinetic Table

Pharmacokinetic: Tables					
No.	Population	IDSL / Example Shell	Title	Programming Notes	Deliverable [Priority]
4.1.	PK	PK01	Summary of GSK2879552 Plasma Pharmacokinetic Concentration-Time Data (Part 1)		SAC [1]

5.7.5. ICH Listings

ICH: Listings					
No.	Population	IDSL / Example Shell	Title	Programming Notes	Deliverable [Priority]
Subject Disposition					
1.	All treated	ES2	Listing of Reasons for Study Withdrawal	ICH E3	SAC [1]
2.	All treated	SD2	Listing of Reasons for Study Treatment Discontinuation	ICH E3	SAC [1]
Protocol Deviations					
3.	All treated	DV2	Listing of Important Protocol Deviations	ICH E3	SAC [1]
4.	All treated	IE3	Listing of Participants with Inclusion/Exclusion Criteria Deviations	ICH E3	SAC [1]
Populations Analysed					
5.	All treated	SP3	Listing of Participants Excluded from Any Population	ICH E3	SAC [1]
Demographic and Baseline Characteristics					
6.	All treated	DM2	Listing of Demographic Characteristics	ICH E3	SAC [1]
7.	All treated	DM9	Listing of Race	ICH E3	SAC [1]
Exposure and Treatment Compliance					
8.	All treated	EX3	Listing of Exposure Data	ICH E3	SAC [1]
Prior and Concomitant Medications					
9.	All treated	AC6	Listing of Prior Anti-Cancer Therapy	ICH E3	SAC [1]
10.	All treated	AC7	Listing of Prior Anti-Cancer Radiotherapy	ICH E3	SAC [1]
11.	All treated	OSP3	Listing of Prior Anti-Cancer Related Surgical Procedures	ICH E3	SAC [1]
12.	All treated	CM3	Listing of Concomitant Medications	ICH E3	SAC [1]

ICH: Listings					
No.	Population	IDSL / Example Shell	Title	Programming Notes	Deliverable [Priority]
13.	All treated	BP4	Listing of Prior Blood Products or Blood Supportive Products	ICH E3	SAC [1]
14.	All treated	BP4	Listing of Blood Products or Blood Supportive Products On Treatment	ICH E3	SAC [1]
Adverse Events					
15.	All treated	AE8	Listing of All Adverse Events	ICH E3	SAC [1]
16.	All treated	AE7	Listing of Subject Numbers for Individual Adverse Events	ICH E3	SAC [1]
Serious and Other Significant Adverse Events					
17.	All treated	AE8	Listing of Fatal Serious Adverse Events	ICH E3	SAC [1]
18.	All treated	AE8	Listing of Non-Fatal Serious Adverse Events	ICH E3	SAC [1]
19.	All treated	AE14	Listing of Reasons for Considering as a Serious Adverse Event	ICH E3	SAC [1]
20.	All treated	AE8	Listing of Adverse Events Leading to Withdrawal from Study / Permanent Discontinuation of Study Treatment	ICH E3	SAC [1]
21.	All treated	AE8	Listing of Other Significant Adverse Events	ICH E3	SAC [1]
All Laboratory					
22.	All treated	LB5	Listing of All Laboratory Data for Participants with Any Value of Potential Clinical Importance/Outside Normal Range	ICH E3	SAC [1]
23.	All treated	LB5	Listing of Laboratory Values of Potential Clinical Importance	ICH E3	SAC [1]
24.	All treated	LB14	Listing of Laboratory Data with Character Results	ICH E3	SAC [1]
25.	All treated	UR2A	Listing of Urinalysis Data for Participants with Any Value of Potential Clinical Importance	ICH E3	SAC [1]
26.	All treated	OAE4	Listing of Dose Limit Toxicity	FDAAA, EudraCT	SAC [1]

CONFIDENTIAL

205744

ICH: Listings					
No.	Population	IDSL / Example Shell	Title	Programming Notes	Deliverable [Priority]
Efficacy					
27.	All treated	EFF_L1	Listing of Investigator-Assessed Responses (with and without confirmation) (IMWG 2016)	ICH E3	SAC [1]
28.	All treated	TTE9	Listing of Duration of Response	ICH E3	SAC [1]
29.	All treated	TTE9	Listing of Progression-Free Survival	ICH E3	SAC [1]
30.	All treated	TTE9	Listing of Overall Survival	ICH E3	SAC [1]
31.	All treated	TTE9	Listing of Time to Response	ICH E3	SAC [1]
Pharmacokinetic					
32	PK	PK07	Listing of GSK2879552 Plasma PK Concentration-Time Data	ICH E3	SAC [1]

